	
Subjects will be randomly assigned to one of the six groups through a computer generated process. A standard permuted-block design will be used for randomization/allocation in order to avoid undesirable differences in the numbers of patients assigned to each group. The randomization schedule will be generated by our statistician using SAS 9.3 PROC PLAN. Variable block sizes will be kept confidential from the protocol to reduce the predictability of the treatment assignments.
 
After screening visit, eligible subjects that are randomized will be assigned a unique subject ID. The subject ID will remain unchanged throughout the study and the nurse will confirm the number at every visit. No single subject will receive more than one subject ID. Blood will be drawn at each follow-up visit to be used in research assays for antibody response, and proteomics evaluation. See blood draw table for timing and volumes of blood draws and assays for which they will be used.
 
In all groups additional blood samples may be taken if required to assess AEs, SAEs, or abnormal laboratory findings.

--	---

Primary Objective:	Immunogenicity 1) To describe the percentage of subjects achieving a protective humoral immune response at 12 months across immunization routes at 7 days post boost.
Primary Endpoints:	Immunogenicity 1) Percentage of subjects in each group with titer of IgG antibodies above the protective limits ($>$ or $=$ 0.5 IU/ml) at 12 months, 7 days after final vaccine dose.
Secondary Objectives:	Immunogenicity 1) To describe the percentage of subjects maintaining a protective humoral immune response at 12 months across immunization routes.
Secondary Endpoint:	Immunogenicity 1) Percentage of subjects in each group with titer of IgG antibodies above the protective limits ($>$ or $=$ 0.5 IU/ml) at 12 months, prior to boost.

Exploratory Objectives	Immunogenicity 1) Describe the cell-mediated immune response to rabies vaccination in groups 1-4. 2) Proteomic characterization of the host response before and after each vaccination to identify biomarkers and correlates of immunity

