---------------------------	--

Statistical Methods:	
This will be a descriptive study to assess immunogenicity of a licensed rabies vaccine using test dosage schedules and routes of administration. No formal statistical hypothesis tests will be conducted. Descriptive analyses will be based on the per-protocol analysis sets.
 
Exploratory statistical analyses of final data may be conducted, if indicated by the descriptive results. Parametric, non-parametric and resampling (bootstrapping) methods for statistical inference may be used in exploratory analyses, based on data compliance with assumptions of methods. P -values ≤ 0.05 will be considered significant and p-values ≤ 0.10 will be considered a trend. Confidence intervals will be constructed at $\alpha=0.05$ and $\alpha=0.10$. When necessary, p-value corrections for multiple comparisons will be applied.
 
Descriptive and any inferential analyses will be carried out using SAS Version 9.2 (or more recent versions), which is licensed and supplied by SAS Institute, Cary, NC, USA.
 
Immunogenicity – Primary objectives:
 
Immunogenicity against rabies virus will be assessed descriptively using the following parameters:
 
Timepoints: Baseline, 28 days after initial dose of rabies vaccine and 7 days after a booster dose given at one year (372 days)
 
 Number and percentage of subjects with a titer ≥ 0.5 IU/ml against rabies virus.
-----------------------------	---

Statistical Methods:	
Immunogenicity –Secondary objectives:
 
Immunogenicity will be assessed descriptively using the following parameters:
 
Time points: Baseline, 28 days and 365 days after initial vaccine dose
 
Percentage of subjects in each group with titer of IgG antibodies above the protective limits (≥ 0.5 IU/ml) at 365 days, prior to boost.

-----------------------------	---

Statistical Methods:	
Calculation of Sample Size:
 
The planned sample size is 60 subjects, who will be randomly allocated (2:2:2:1:1) to four treatment groups and two control groups (i.e. 12 subjects in groups 1, 2, 3, and 4 and 6 subjects in groups 5 and 6). The sample size was chosen empirically, based on sample sizes of other exploratory studies of this general type. The study is not powered to test non-inferiority or equivalency in immunogenicity among groups according to vaccination dosage and route of administration.

-----------------------------	---

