1.5 Rationale

Antibody Assays: The rabies virus envelope glycoprotein G is the correlate for protective immunity and by World Health Organization (WHO) guidelines, an antibody titer for protection should be greater than or equal to 0.5 IU/ml. Several studies have demonstrated the high sensitivity and specificity of the Bio-Rad, enzyme-linked immunosorbent assay (ELISA), PLATELIA RABIES II® and correlation to the current reference method, rapid fluorescent focus inhibition test (RFFIT) (5, 6). The Bio-Rad Platelia Rabies II assay will be used to assess subjects' immune response to rabies vaccine.

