16.2 Secondary Endpoints

16.2.1 Immunogenicity Endpoints

- 1) Total IgG and neutralizing Ab levels, measured by ELISA and PRNT, against rabies virus at baseline and at 28 days 1 month and 365 days post-initial vaccine dose.

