20.1 Statistical Methods for Primary Immunogenicity Objectives

Immunogenicity against rabies will be assessed descriptively using the following

parameters:

Timepoints: At baseline, 28 days and 372 days.

- Number and percentage of subjects with a titer ≥ 0.5 IU/ml against rabies virus by treatment group at days 28 and 372.

The descriptive statistics listed above will be calculated for each of the six groups for each blood draw. Descriptive results will be reported in tabular and graphic formats. A separate document, the statistical analysis plan (SAP) will be developed prior to data analysis. It will provide more detailed information about the specific descriptive statistics to be used and the format (tables, listings and figures) by which the statistics will be reported.

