20.2 Statistical Methods for Secondary Immunogenicity Objectives

Immunogenicity will be assessed descriptively using the following parameters:

Timepoints: Day 28 and day 365.

The descriptive statistics listed above will be calculated for each of the six groups for the time points stated above. Specification of statistics and reporting formats will be provided in the SAP, as described above.

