Timepoints: At baseline, 28 days and 372 days.

- Number and percentage of subjects with a titer ≥ 0.5 IU/ml against rabies virus by treatment group at days 0, 28 and 372.

A table that presents the total number of per-protocol subjects and the number and percent of each treatment group who have a titer ≥ 0.5 IU/ml against rabies virus at days 0, 28 and 372 will be produced.

Statistical Methods for Secondary Immunogenicity Objectives

Immunogenicity will be assessed descriptively using the following parameters:

Timepoints: Days 0, 28 and 365.

A table that presents, by treatment group, the total number of per protocol subjects and the number and percent of each group who have IgG titers ≥ 0.5 IU/ml against rabies virus at days 0, 28 and 365 will be produced.

Statistical Methods for Adverse Events and Serious Adverse Events

For each treatment group, a line listing by subject that describes adverse events and post-baseline day of occurrence of the AE will be produced.

The number and percent of subjects in each group who reported any AE between Days 0 and 372 will be summarized in tabular format.

A table showing the number and percentage of subjects in each group who reported adverse events by general type (category) of event will be produced.

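### The protocol gives two different secondary endpoints; the SAP follows the synopsis, so the antibody levels in 16.2.1 have no planned table, and no confidence interval is tied to the percentages

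*SAP*

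**What the plan says.** **Secondary endpoint, protocol body.** Section 16.2.1 reads "Total IgG and neutralizing Ab levels, measured by ELISA and PRNT, against rabies virus at baseline", and adds Day 28 and Day 365.

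**Secondary endpoint, synopsis.** The Secondary Endpoint row gives the percentage of each group at or above "0.5 IU/ml) at 12 months, prior to boost". The synopsis Statistical Methods row repeats this as a percentage at or above "0.5 IU/ml) at 365 days, prior to boost".

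**Statistics, protocol.** Section 20.2 states that "The descriptive statistics listed above will be calculated for each of the six groups for the time points stated above". The only statistic above it is in Section 20.1: the count and percentage with a titer of at least 0.5 "IU/ml against rabies virus by treatment group at days 28 and 372". Section 20.2 then defers: "Specification of statistics and reporting formats will be provided in the SAP, as described above".

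**Statistics, SAP.** The secondary section plans one table, showing "the number and percent of each group who have IgG titers" of at least 0.5 IU/ml at Days 0, 28 and 365. The primary section plans the same kind of table for Days 0, 28 and 372. Neither mentions an interval, a GMT or an assay.

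**Traces of a level analysis.** The SAP section on missing data and outliers, and Protocol 21.1, give conversion rules for GMTs, fold-rise and titer ratios. The SAP section on analysis populations, and Protocol 20.5, assign a kinetic analysis to the full analysis set (FAS). Neither document says what that analysis contains.

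**Assay.** Protocol 1.5 says "The Bio-Rad Platelia Rabies II assay will be used to assess" the immune response. Section 3 (Laboratory) assigns titers by RFFIT to an outside laboratory. Section 16.2.1 names ELISA and PRNT.

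**Intervals.** The SAP Statistical Methods section and Protocol 20 mention intervals at alpha 0.05 and 0.10. The sentence stands in the paragraph on exploratory analyses that may be done if the descriptive results suggest them. It names no parameter, method or table.

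**The concern.** If the SAP is followed exactly, an endpoint listed in the protocol body goes unreported. A reader of the final report could not tell whether levels were dropped by decision or by oversight.

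Levels bear on the trial's own question. Protocol 2.2 sets persistence of the humoral response as the secondary objective, and Protocol 1.2 says current rabies vaccines produce an antibody response in 100% of individuals. If the percentages sit near that ceiling, particularly after the boost, they cannot separate the schedules, whereas levels might.

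Precision matters for a related reason. The Introduction looks for a shorter series that is equally effective, so readers will compare percentages across groups of 12. With no hypothesis tests and an empirically chosen sample size, an interval is the direct way to show how little similar percentages prove.

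**Working it through.** **1. Does any planned output cover the 16.2.1 endpoint?**

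| Source | Secondary measure | Time points |
|---|---|---|
| Protocol 16.2.1 | Levels: total IgG and neutralizing antibody | Baseline, Day 28, Day 365 |
| Synopsis, Secondary Endpoint | Percentage ≥0.5 IU/ml | 12 months, before boost |
| Synopsis, Statistical Methods | Percentage ≥0.5 IU/ml | Baseline, Days 28 and 365 listed; percentage specified at Day 365 |
| Protocol 20.2 | Refers back to 20.1 (count and percentage); defers to SAP | Days 28, 365 |
| SAP, secondary section | Count and percentage, IgG ≥0.5 IU/ml | Days 0, 28, 365 |

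The chain from 16.2.1 through 20.2 to the SAP ends in a percentage. No table, summary statistic or time point is given for levels.

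**2. Group sizes.** The stated total reproduces: 4 × 12 + 2 × 6 = 60. The blood draw tables for Groups 5 and 6 list proteomics only, so the titer tables in practice concern Groups 1–4. Withdrawn subjects are not replaced (Protocol 6.8), so 12 per group is a ceiling.

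**3. Precision of a percentage.** When all n subjects respond, the exact (Clopper-Pearson) 95% lower limit is 0.025^(1/n). For n = 12 this is 0.025^(1/12) = 0.735. Other limits come from beta quantiles. Response counts, and any n below 12, are illustrative.

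| Result | Exact 95% CI |
|---|---|
| 12/12 | 73.5–100% |
| 11/12 | 61.5–99.8% |
| 10/12 | 51.6–97.9% |
| 6/12 | 21.1–78.9% |
| 10/10 (two assumed per-protocol exclusions) | 69.2–100% |

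Wilson limits for 12/12 are 75.8–100%, so the choice of method does not change the message.

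**4. Precision of a GMT.** The 95% interval runs from the GMT divided by F to the GMT multiplied by F, with F = 10^(t × SD/√n), where t is the 97.5% point on n − 1 degrees of freedom and SD is on the log10 scale. For n = 12 and SD 0.4, F = 10^(2.201 × 0.4/3.464) = 1.80. The documents give no SD, so a range is shown.

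| Assumed log10 SD | F, n = 12 | F, n = 10 |
|---|---|---|
| 0.3 | 1.55 | 1.64 |
| 0.4 | 1.80 | 1.93 |
| 0.5 | 2.08 | 2.28 |
| 0.6 | 2.41 | 2.69 |

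**5. Timing.** The SAP is version 1.1, dated 5 December 2016. The synopsis and Protocol 5.4 plan assay completion for July 2016 and label their dates as approximate (5.4). The trial is open-label.

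**The case against.** The best defence is that the SAP did follow the protocol, because the synopsis defines the secondary endpoint as a percentage twice. That stands. A reader might infer that the SAP dropped a protocol endpoint; the documents support only a contradiction inside the protocol, which the SAP resolves one way without saying so.

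It can also be said that levels are not ignored. The GMT and titer-ratio rules, the outlier procedures and the kinetic analysis make sense only for levels. This too stands, so it would be wrong to say that the plan never considered them. But handling rules are not an analysis: no table or time point follows from them.

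On intervals, the shared sentence says that they will be constructed, and tying it to exploratory work rests on where it sits. That reading is fair but not the only one, so a claim that the SAP has no intervals would be false. The tables give N, count and percentage, so a reader could compute an interval, and the protocol already says that the study is not powered for non-inferiority or equivalence. The interval part is therefore a reporting improvement.

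Three further inferences are not supported. The study is descriptive with an empirical sample size, so this is not a power error. The SAP's date does not show that levels were dropped after results were seen: the calendar is approximate, and the documents do not say when results became available. The rule that caps titers at the upper limit of quantification could lower a GMT, but no size can be given, because the documents state neither the spread of titers nor the share above that limit.

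**Conclusion.** The point holds as a gap in specification that should be corrected. The synopsis and 16.2.1 disagree on the secondary endpoint, the SAP follows the synopsis, and the two level measures in 16.2.1 have no planned table. The assay behind the titers is also unsettled, which affects percentages and levels alike. The primary percentages can still be produced.

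On size, one protocol endpoint with two measures at three time points would go unreported. The lesser point about intervals rests on the documented group size of 12, where a perfect result is still compatible with a true rate of about 74%. Other response counts, smaller per-protocol numbers and all SDs are assumptions.

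**What to change.** 1. **Reconcile the endpoint.** Make the synopsis and 16.2.1 agree, and state which assay supplies each measure, resolving Sections 1.5, 3 and 16.2.1.
2. **Keep levels and plan them.** Add to the SAP a GMT table for Groups 1–4 with log-scale 95% intervals at Days 0, 28 and 365, on the per-protocol sets already specified for those days. Give one panel for each 16.2.1 measure that was assayed, and say so if one was not. Show the numbers below LLOQ and above ULOQ beside each GMT, because both are replaced by fixed values.
3. **Settle the kinetic analysis.** Define it separately on the FAS as GMT by visit over all antibody sampling visits, or delete it from both Protocol 20.5 and the SAP.
4. **If levels are dropped instead,** amend 16.2.1, Protocol 20.5 and 21.1 and the matching SAP text together. Record whether assay results were already available at that point.
5. **Secondary recommendation.** Add an exact (Clopper-Pearson) 95% interval to each percentage for Groups 1–4 in both SAP titer tables, and name the method.

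The cost is one protocol clarification, SAP wording, one table and interval columns, using samples already in the visit schedule. No new laboratory work is required: if the second assay was not run, the report says so. The GMT table must wait until the assay is settled, and it is less informative at visits with many values beyond the quantification limits. The report becomes longer and shows wider uncertainty.

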Group	Schedule of Vaccination and Blood Draw								
1	
Vaccinations: Rabies vaccine IM 3 doses.
 
Blood samples: Blood samples will be taken for research assays evaluating, humoral immunity, cell mediated immunity, and proteomics. See Blood Draw Table: Group 1 for timing of blood draws.
 
Total blood volume for Group 1: approx 593 mL
								
2	
Vaccinations: Rabies vaccine ID 3 doses
 
Blood samples: Blood samples will be taken for research assays evaluating humoral immunity, cell mediated immunity, and proteomics. See Blood Draw Table: Group 2 for timing of blood draws.
 
Total blood volume for Group 2: approx 593 mL
								
3	
Vaccinations: Rabies vaccine IM 2 doses
 
Blood samples: Blood samples will be taken for research assays evaluating humoral immunity, cell mediated immunity, and proteomics. See Blood Draw Table: Group 3 for timing of blood draws.
 
Total blood volume for Group 3: approx 510 mL
								

	4	
Vaccinations: Rabies vaccine ID 2 doses
 
Blood samples: Blood samples will be taken for research assays evaluating humoral immunity, cell mediated immunity, and proteomics. See Blood Draw Table: Group 4 for timing of blood draws.
 
Total blood volume for Group 4: approx 510 mL

	5	
Vaccination: Placebo IM 1 dose
 
Blood Samples: Blood samples will be taken for research assays evaluating proteomics. See Blood Draw Table: Group 5 for timing of blood draws.
 
Total blood volume for Group 5: approx 9 mL

	6	
Vaccination: Placebo IM 1 dose
 
Blood Samples: Blood samples will be taken for research assays evaluating proteomics. See Blood Draw Table: Group 6 for timing of blood draws.
 
Total blood volume for Group 6: approx 9 mL

Duration of the Trial:	The expected duration of a subject's participation in the trial will be 13 months for subjects in Groups 1, 2, 3, and 4. In groups 5 and 6 participation will end after Day 7.
Licensed Product:	RabAvert® Rabies Vaccine
Form:	RabAvert®: ≥2.5 units [contains albumin (human), amphotericin B (may have trace amounts), bovine gelatin, chicken egg protein, chlortetracycline (may have trace amounts), neomycin (may have trace amounts); PCEC; grown in chicken fibroblast culture; supplied with diluent].

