Vaccination		X		X					X	
AE and SAE		X	X	X	X	X	X	X	X	X

Blood Draw Table: Group 4
Rabies vaccine at Day 0 and Day 7

Day	0	3	7	10	14	28	77	365	372
	VAC		VAC					Boost	
Antibody Assays/ Proteomics	4 x 8.5 ml	1 x 3 ml	2 x 8.5 ml	1 x 3 ml	2 x 8.5 ml	2 x 8.5 ml	2 x 8.5 ml	4 x 8.5 ml	4 x 8.5 ml
CMI	8 x 8.0 ml	2 x 8.0 ml	5 x 8.0 ml	2 x 8.0 ml	5 x 8.0 ml	5 x 8.0 ml	5 x 8.0 ml	8 x 8.0 ml	3 x 8.0 ml
Daily BV	98 ml	19 ml	57 ml	19 ml	57 ml	57 ml	57 ml	98 ml	58 ml
CBV (Total)	98 ml	117 ml	174 ml	193 ml	250 ml	307 ml	364 ml	462 ml	520 ml
Total (56 days)						307 ml	57 ml	98 ml	156 ml

Study Procedures: Group 5 (control)
6 Subjects, 4 Visits, 7 Day Duration Per Subject

Study Day	-60 to 0	0	3	7
Visit Type	Screening	VAC BL	BL	BL
Time windows (days)	-60 to 0	0	+/-1	+/-1
Informed consent/IC review	X	X		
Inclusion/exclusion criteria	X	X		
Contraindications	X	X		
Significant medical history	X			
Physical Exam	X			
Targeted PE		X	X	X
Vital signs	X	X	X	X
Urine pregnancy test *Females	X*	X*		
Concomitant therapy	X	X	X	X
Demography	X			
Randomization		X		
Blood Draw for Research Assays		X	X	X
Vaccination		X		
AE and SAE		X	X	X

Blood Draw Table: Group 5
Human Serum Albumin at Day 0

Day	0	3	7
	VAC		
Proteomics	1 x 3 ml	1 x 3 ml	1 x 3 ml
Daily BV	3 ml	3 ml	3 ml
CBV (Total)	3 ml	6 ml	9 ml

Study Procedures: Group 6 (control)
 6 Subjects, 4 Visits, 7 Day Duration Per Subject

Study Day	-60 to 0	0	3	7
Visit Type	Screening	VAC BL	BL	BL
Time windows (days)	-60 to 0	0	+/-1	+/-1
Informed consent/IC review	X	X		
Inclusion/exclusion criteria	X	X		
Contraindications	X	X		
Significant medical history	X	X		
Physical Exam	X			
Targeted PE		X	X	X
Vital signs	X	X	X	X
Urine pregnancy test *Females	X*	X*		
Concomitant therapy	X	X	X	X
Demography	X			
Randomization		X		
Blood Draw for Research Assays		X	X	X
Vaccination		X		
AE and SAE		X	X	X

Blood Draw Table: Group 6
Human Serum Albumin at Day 0

Day	0	3	7
	VAC		
Proteomics	1 x 3 ml	1 x 3 ml	1 x 3 ml
Daily BV	3 ml	3 ml	3 ml
CBV (Total)	3 ml	6ml	9 ml

List of Terms and Abbreviations

Ab	antibody
ADR	adverse drug reaction
AE	adverse event
AESI	adverse event of special interest
AR	adverse reaction
BL	blood sample visit
C	Celsius
CDM	Clinical Data Management
CI	confidence interval
CIOMS	Council for International Organizations of Medical Sciences
CMI	Cell Mediated Immunity
CRA	Clinical Research Associate
CSTE	Council of State and Territorial Epidemiologists
D	day
eCRF	electronic case report form
EDC	electronic data capture

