5.2 Trial Plan

Eligible subjects will be identified and recruited. Each subject must sign and date the informed consent form before any procedure or treatment associated with the study is performed.

Depending on group assignment, subjects will receive vaccination in accordance with the schedule outlined in Table 2 above. There will be follow-up visits for review of adverse events and collection of blood samples.

Blood samples will be collected at Day 0 and at various time points throughout the study to test the immune response to rabies. Additional blood samples will be collected at different time points to evaluate the immune response to rabies vaccination. Additional biological samples (e.g. body fluids, tissue samples) may be collected in the event of an SAE.

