Exploratory statistical analyses of final data may be conducted, if indicated by the descriptive results. Parametric, non-parametric and resampling (bootstrapping) methods for statistical inference may be used in exploratory analyses, based on data compliance with assumptions of methods. P -values ≤ 0.05 will be considered significant and p-values ≤ 0.10 will be considered a trend. Confidence intervals will be constructed at $\alpha=0.05$ and $\alpha=0.10$. When necessary, p-value corrections for multiple comparisons will be applied.

A descriptive summary of adverse events that were reported throughout the trial will be produced.

Descriptive and inferential analyses (if any) will be carried out using SAS Version 9.2 (or more recent versions), which is licensed and supplied by SAS Institute, Cary, NC, USA.

Per-Protocol Analysis Set

The Per-Protocol (PP) analysis set will include all subjects who had no protocol deviations at the time that the data was collected. Three PP analysis sets will be produced for the primary objective that will contain separate data from blood drawn on day 0, day 28 and day 372, respectively. Descriptive analysis of the secondary endpoint will require a fourth per protocol analysis set for blood drawn on day 365. Subjects will be excluded from the PPAS for the following reasons:

1. Subject did not meet all protocol-specified inclusion/exclusion criteria or definitive contraindications (only for the second and third vaccination)
2. Subject did not receive the correct number of injections
3. Administration of vaccine was not done as per protocol (site and route of administration)
4. Subject did not receive vaccine in the proper time window defined in the tables of the study procedures
5. Subject did not provide a post-dose serology sample in the proper time window defined in the tables of the study procedures

Subjects will remain in this population as long as they do not meet one of the above criteria, except for blood sampling timing and validity of the serology test result*. A PP set will be defined for each injection.

***Note:** For example, a subject whose time period is outside the defined visit window only between the first injection and the blood sample taken after the first injection will be excluded from PP1 but may be kept in PP2 or PP3.

Subjects will be analyzed by the vaccine group to which they were randomized, subject to the exclusion criteria above

Full Analysis Set

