The full analysis set (FAS) is defined as the subjects who received at least one injection of Rabies vaccine and had at least one blood sample drawn and valid post-injection serology result (i.e. a result different from “NR” or missing).

Subjects will be analyzed by the treatment group to which they were randomized.

Populations Used in Analyses

The immunogenicity analysis will be performed on the PP. The kinetic analysis will be performed on the FAS.

Handling of Missing Data and Outliers

Immunogenicity

For the computation of GMTs, a titer reported as < LLOQ will be converted to a value of 0.5 LLOQ.

For calculating fold-rise and titer ratio (GMTR), < LLOQ will be converted to 0.5 LLOQ for a numerator and < LLOQ will be converted to LLOQ for a denominator

Any titer reported as > ULOQ (upper limit of quantization) will be converted to ULOQ.

Missing data will not be imputed.

Potential outliers will be identified using histograms and modified box plots or normal probability plots, when appropriate. Choice of subsequent tests for outliers (e.g. Grubbs, Tietjen-Moore and ESD) will depend on the number and nature of suspected outliers and may require data transformation. .
Bootstrapped estimates of standard errors may also be reported. Sensitivity analysis of effect of outliers on descriptive statistics will be conducted, and if necessary descriptive statistics that include and exclude outliers will be reported

Statistical Methods for Baseline Comparisons

Mean (SD) and median (IQR) age at baseline will be computed and descriptively compared across the six groups. Results will be presented in tabular format.

The number and percentage of males and females per group at baseline will be calculated and results will be presented in tabular format.

Baseline mean (SD) and median (IQR) of all other quantitative demographic variables of interest will be calculated for each group and the results will be presented in a table.

The number and percentage per group at baseline of all other qualitative demographic variables of interest will be calculated for each group and the results will be presented in tabular format.

Statistical Methods for Subject Disposition

For each group, the number and percentage of subjects who received a total of 0, 1, 2, 3 and 4 rabies vaccinations will be reported in tabular format.

Statistical Methods for Primary Immunogenicity Objectives

Immunogenicity against rabies will be assessed descriptively using the following parameters:

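### Minor: the SAP reports the percentage with any AE over Days 0 to 372 for each group, but control Groups 5 and 6 are followed only to Day 7, so vaccine and control percentages are not on a common basis.

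*SAP*

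**What the plan says.** The SAP section Statistical Methods for Adverse Events and Serious Adverse Events plans three outputs.

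- A line listing by subject for each treatment group, giving the post-baseline day of each AE.
- An any-AE table: "The number and percent of subjects in each group who reported any AE between Days 0 and 372 will be summarized in tabular format".
- By-category results, giving "the number and percentage of subjects in each group who reported adverse events by general type (category) of event", for which no time window is stated.

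The general SAP text adds only this: "A descriptive summary of adverse events that were reported throughout the trial will be produced".

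On follow-up, the protocol synopsis (Duration of the Trial) gives 13 months for Groups 1 to 4 and then says: "In groups 5 and 6 participation will end after Day 7". The study procedures table for each control group is headed "6 Subjects, 4 Visits, 7 Day Duration Per Subject" and marks AE/SAE collection at Days 0, 3 and 7. Protocol section 9 gives each control subject one injection of human serum albumin. AEs are not confined to the 30 minutes after injection, since section 5.2 says: "There will be follow-up visits for review of adverse events and collection of blood samples".

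The SAP's subject disposition section reports "the number and percentage of subjects who received a total of 0, 1, 2, 3 and 4 rabies vaccinations" for each group. The Full Analysis Set is built on "the subjects who received at least one injection of Rabies vaccine" together with a valid post-injection serology result. The AE section names no analysis set.

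**The concern.** A percentage of subjects with any AE rises with the time, injections and visits over which AEs can arise and be recorded. Set side by side under one Day 0 to 372 label, the control columns would look safer simply because those subjects were observed for a week. The by-category table has the same defect and does not even name a window.

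Nothing else in the SAP corrects this. The disposition table counts rabies vaccinations only, so controls fall under zero, and neither their albumin injection nor their follow-up time appears. The Full Analysis Set could not supply the AE denominator, because by design none of the 12 controls receives rabies vaccine or has a serology result. Protocol section 18.2 does not extend AE capture either: after completion it covers only SAEs likely to be related to the product or the experiment.

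At stake is a safety table that a reader could take as evidence of more AEs with vaccine when the gap reflects follow-up alone.

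**Working it through.** The plan gives no figure of its own to reproduce, and the documents contain no AE rate.

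**Inputs (protocol study procedures tables; sections 5 and 9)**

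| | Groups 1, 2 | Groups 3, 4 | Groups 5, 6 |
|---|---|---|---|
| Subjects per group | 12 | 12 | 6 |
| Last visit | Day 372 | Day 372 | Day 7 |
| Injections, including the Day 365 boost | 4 | 3 | 1 |
| AE visit days | 0, 3, 7, 10, 14, 21, 24, 28, 77, 365, 372 | 0, 3, 7, 10, 14, 28, 77, 365, 372 | 0, 3, 7 |
| AE visits | 11 | 9 | 3 |

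**Planned observation**

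- Per subject: 372 / 7 = 53.1. Controls are seen for 7 / 372 = 1.9% of the labelled window.
- In total: Groups 1 to 4, 48 × 372 = 17,856 subject-days; Groups 5 and 6, 12 × 7 = 84. The control share is 84 / (17,856 + 84) = 0.5%. This share also reflects the smaller control groups; the per-subject ratio is what distorts a percentage.

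**Illustration with no vaccine effect.** Let p be the assumed proportion of a vaccine group with any AE by Day 372, and f the control group's share of that group's exposure. If the risk of a first AE accrues evenly over that exposure, the expected control proportion is 1 − (1 − p)^f.

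| Basis for f | f | p = 20% | p = 50% | p = 80% |
|---|---|---|---|---|
| Calendar time | 7/372 | 0.4% | 1.3% | 3.0% |
| Injections, against Groups 1, 2 | 1/4 | 5.4% | 15.9% | 33.1% |
| Visits, against Groups 1, 2 | 3/11 | 5.9% | 17.2% | 35.5% |
| Injections (1/3) or visits (3/9), against Groups 3, 4 | 1/3 | 7.2% | 20.6% | 41.5% |

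For example, 1 − 0.5^(1/4) = 15.9%. In every cell the control figure is well below p, so the direction does not depend on which basis is chosen. The size does.

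**Precision in any window.** With no events in n subjects, the exact two-sided 95% upper limit is 1 − 0.025^(1/n). That is 45.9% for 0 of 6 and 26.5% for 0 of 12.

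**The case against.** - **The AE tables may not include the controls.** The SAP does not list the groups in its AE section, and the synopsis separates four treatment groups from two control groups. The SAP's titre tables are also by treatment group, and controls cannot fill those. If the AE tables covered Groups 1 to 4 only, the mismatch would vanish. But the SAP's baseline section speaks of six groups, its disposition table has a category for zero rabies vaccinations, and protocol section 22 counts six treatment groups. Inclusion is the natural reading. The inconsistent wording is one more reason for the SAP to say so.
- **No such contrast is planned.** This stands. The trial compares schedules and routes among Groups 1 to 4, which share the Day 372 endpoint. The controls serve the proteomic analysis (protocol section 5.1), there is no safety objective, and no formal tests are planned. It limits the consequence, but a descriptive table must still describe what was observed.
- **The listing already gives AE days.** It does, but it gives neither each group's follow-up nor an early-window summary.
- **The size rests on assumed rates, and a Day 0 to 7 table with six controls per route would say little.** Both points stand. Only the day, injection and visit counts are documented. With a window of plus or minus one day, the Day 7 visit also falls anywhere from Day 6 to Day 8, so an early window is only approximately common.

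**Conclusion.** The concern holds and is minor. Followed as written, the SAP gives two of its six groups a Day 0 to 372 AE percentage based on 7 days of follow-up, and those percentages are not comparable with the vaccine groups'. The documented imbalance per subject is 372 against 7 days, four or three injections against one, and 11 or nine AE visits against three. The bias runs against vaccine on each of these bases. Its size in percentage points cannot be known from the documents: across assumed vaccine-group proportions of 20% to 80%, the no-effect control figure runs from 0.4% to 41.5%.

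The conclusion assumes that the AE tables cover all six groups. The damage is confined to how the AE tables read; no primary or secondary immunogenicity result is affected.

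**What to change.** In the SAP's adverse event section:

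1. **Add one short any-AE and by-category summary on a common early window.** Include all subjects injected with vaccine or albumin, from the first injection up to the Day 7 visit, or to Day 7 if that visit is missed. Groups 1 to 4 are due their second dose on that visit date and the listing records only the day, so apply one rule to all six groups, for example a separate row for onsets on the visit date. Show it by group or by route (Groups 1 and 3, 2 and 4, 5, 6), with a footnote that it is descriptive and imprecise with six controls per route.
2. **Relabel the Day 0 to 372 tables, including the by-category table.** Either put Groups 5 and 6 under their own Day 0 to 7 heading, or footnote each group's follow-up, number of injections and number of AE visits. Every control AE should stay in a summary table.
3. **State the AE denominator** as all injected subjects, and say that all six groups are included.

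If only one change is made, the footnote in item 2 is the minimum. The cost is one small table and a footnote, drawn from onset days the trial already plans to record. The drawback is wide uncertainty in the extra table.
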